APPENDIX I – SORAFENIB DOSING NOMOGRAM

AAML1031 Sorafenib Dosing Nomogram			
BSA Range (m ²)	Dose Level 0 100 mg/m ² /day once daily (DOSE/WEEK)	Dose Level 1 200 mg/m ² /day once daily (DOSE/WEEK)	Dose Level 2 300 mg/m ² /day divided BID (DOSE/WEEK)
≤ 0.35	50 mg x 4 days/week, 0 x 3 day/week (200 mg)	50 mg x 5 days/week, 100 mg x 2 days/week (450 mg)	50 mg twice daily x 7 days/week (700 mg)
0.36 - 0.4	50 mg x 5 days/week, 0 x 2 day/week (250 mg)	50 mg x 4 days/week, 100 mg x 3 days/week (500 mg)	50 mg twice daily x 6 days/week + 100 mg twice daily x 1 day/week (800 mg)
0.41 - 0.45	50 mg x 6 days/week, 0 x 1 day/week (300 mg)	50 mg x 2 days/week, 100 mg x 5 days/week (600 mg)	50 mg twice daily x 5 days/week + 100 mg twice daily x 2 days/week (900 mg)
0.46 - 0.55	50 mg x 7 days/week (350 mg)	100 mg x 7 days/week (700 mg)	50 mg q AM +100 mg q PM x 7 days/week (1050 mg)
0.56 - 0.6	50 mg x 6 days/week, 100 mg x 1 day/week (400 mg)	100 mg x 6 days/week, 200 mg x 1 day/week (800 mg)	50 mg twice daily x 2 days/week + 100 mg twice daily x 5 days/week (1200 mg)
0.61 - 0.7	50 mg x 5 days/week, 100 mg x 2 days/week (450 mg)	100 mg x 5 days/week, 200 x 2 days/week (900 mg)	100 mg twice daily x 7 days/week (1400 mg)
0.71 - 0.8	50 mg x4 days/week, 100 mg x3 days/week (500 mg)	150 mg x 7 days/week (1050mg)	100 mg twice daily x 5 days/week + 150 mg twice daily x 2 days/week (1600 mg)
0.81 - 0.9	50 mg x 2 days/week, 100 mg x 5 days/week (600 mg)	150 mg x 4 days/week, 200 mg x 3 days/week (1200 mg)	100 mg q AM + 150 mg q PM x 7 days/week (1750 mg)
0.91 - 1.05	100 mg x 7 days/week (700 mg)	200 mg x 7 days/week (1400 mg)	150 mg twice daily x 7 days/week (2100 mg)
1.06 - 1.2	100 mg x 6 days/week, 200 mg x1 day/week (800 mg)	200 mg x 3 days/week. 250 mg x 4 days/week (1600 mg)	150 mg q AM + 200 mg q PM x 7 days/week (2450 mg)
1.21 - 1.35	100 mg x 5 days/week, 200 mg x 2 days/week (900 mg)	250 mg x 7 days/week (1750 mg)	200 mg twice daily x 7 days/week (2800 mg)
1.36 - 1.6	100 mg x 4 days/week, 200 mg x 3 days/week (1000 mg)	300 mg x 7 days/week (2100 mg)	200 mg q AM + 250 mg q PM x 7 days/week (3150 mg)
1.61 - 1.7	100 mg x 2 days/week, 200 mg x 5 days/week (1200 mg)	350 mg x 7 days/week (2450 mg)	250 mg twice daily x 7 days/week (3500 mg)
1.71 - 1.85	100 mg x 1 day/week, 200 mg x 6 days/week (1300 mg)	350 mg x 3 days/week 400 mg x 4 days/week (2650 mg)	250 mg q AM + 300 mg q PM x 7 days/week (3850 mg)
≥ 1.86	200 mg x 7 days/week (1400 mg)	400 mg x 7 days/week (2800 mg)	300 mg twice daily x 7 days /week (4200 mg)

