5.2 Induction 1 for FLT3-ITD patients – ADE (10+3+5) with GO with Sorafenib

The following therapy guidelines are for patients during Induction I with FLT3-ITD mutation. Patients on Induction I will receive gemtuzumab in addition to ADE therapy based on GO genotyping. Induction I lasts a total of 28 days.

Intrathecal Cytarabine: IT

Given at time of diagnostic lumbar puncture or Day 1.

Age-based dosing:

Age (yrs)	Dose
0-0.99	20 mg
1-1.99	30 mg
2-2.99	50 mg
≥ 3	70 mg

For CNS positive patients: add twice weekly IT AraC doses until CNS is clear, plus two additional treatments. A minimum of four intrathecal treatments are to be administered during the period of three weeks following diagnosis.

Cytarabine: Slow IV Push (e.g., over 1-2 minutes)

100 mg/m²/dose (3.3 mg/kg/dose if BSA < 0.6 m²) every 12 hours (total of 20 doses) on Days 1-10.

Daunorubicin (DAUN): IV over 15 minutes

50 mg/m²/dose (1.67 mg/kg/dose if BSA < 0.6 m²) every other day (total of 3 doses) on Days 1, 3, 5.

See Section 6 if direct bilirubin is > 2.

Etoposide (ETOP): IV over 60 – 120 minutes

100 mg/m²/dose (3.3 mg/kg/dose if BSA < 0.6 m²) daily (total of 5 doses) on Days 1-5.

See Section 6 if direct bilirubin is > 2.

Gemtuzumab Ozogamicin (GO): IV over 2 hours

3 mg/m²/dose (0.1 mg/kg/dose if BSA < 0.6 m²) once (total of 1 dose) on Day 6 through 10.

GO to be given once when GO genotyping demonstrates CC genotype. It can be given on any day between days 6-10 of Induction 1.

Pre-medicate with an antihistamine such as diphenhydramine, 1 mg/kg IV (max 50 mg), acetaminophen 10-15 mg/kg PO (max 650 mg) and methylprednisolone (1mg/kg) PO/IV. Repeat every 4 hours as needed to prevent post infusion complications.

Sorafenib (SORAF): PO

Days: 11 through 28.

Dose: 200 mg/m²/dose daily, rounded to accommodate tablet size. The maximum dose will be 400 mg. Dose will be administered per dosing nomogram in Appendix I.

Note: Sorafenib tablets should be taken at least 1 hour before or 2 hours after food. Tablets should be taken with clear liquids (approximately 2 to 4 ounces for children < 12 years and 4 to 8 ounces for \geq 12 years). If taken with food, sorafenib should be taken with a moderate to low fat meal. Tablets should not be crushed and should be swallowed whole. However, sorafenib tablets can be dispersed in water to facilitate the administration to subjects that cannot swallow tablets

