Dose: 200 mg/m²/dose daily, rounded to accommodate tablet size. The maximum dose will be 400 mg.

Dose to be administered per dosing nomogram in Appendix I.

Note: Sorafenib tablets should be taken at least 1 hour before or 2 hours after food. Tablets should be taken with clear liquids (approximately 2 to 4 ounces for children < 12 years and 4 to 8 ounces for \geq 12 years). If taken with food, sorafenib should be taken with a moderate to low fat meal. Tablets should not be crushed and should be swallowed whole. However, sorafenib tablets can be dispersed in water to facilitate the administration to subjects that cannot swallow tablets.

Patients with FLT3-ITD AML may proceed to best allogenic donor SCT or alternative donor SCT following Induction II. Depending on timing, these patients may receive a third course of chemotherapy (Intensification I) prior to HSCT. This course could be either AE or HD ARAC/LASP with sorafenib.

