6.3 Cardiac Toxicity

6.3.1 Left Ventricular Systolic Dysfunction:

Daunorubicin, mitoxantrone, and sorafenib will be held if there is significant evidence of cardiac disease by echocardiogram (shortening fraction < 28% or EF < 55%). Cardiac examination with echocardiogram is required prior to the start of all chemotherapy courses, at the end of protocol therapy, and in follow up. Echocardiogram and cardiac biomarker evaluation (i.e. troponin) are also strongly recommended, particularly in clinical scenarios with potential or suspected cardiac dysfunction.

6.3.2 Daunorubicin and Mitoxantrone:

Do not re-start anthracyclines if held for left ventricular shortening dysfunction that is not associated with a microbiologically proven bacteremia or sepsis. If the left ventricular shortening dysfunction occurred in the setting of microbiologically proven bacteremia or sepsis, then anthracyclines may be reinstated at the treating clinician's discretion once the shortening fraction has returned to $\geq 28\%$ or $EF \geq 55\%$.

6.3.3 Sorafenib in Combination with Chemotherapy:

Sorafenib should be held for a shortening fraction of $< 28\%$ or $EF < 55\%$ regardless of attribution. Sorafenib should be restarted at a reduced dose (100 mg/m^2) when the shortening fraction has returned to $\geq 28\%$ or $EF \geq 55\%$. If SF decreases below

28% or EF decreases below 55% on 100 mg/m², then sorafenib should be discontinued permanently. Sorafenib dose may not be re-escalated in combination with chemotherapy.

6.3.4 Hypertension:

The table below will be used to manage hypertension possibly, probably or definitely related to sorafenib. Management of hypertension not related to sorafenib is at the treating clinician's discretion. Should initiation of anti-hypertensive (anti-HTN) therapy be required, single agent therapy (such as amlodipine or nifedipine) should be started. For patients greater than age 18, rely on CTCAE v.5.0 grading of hypertension for consideration of dose adjustment.

GRADE	MANAGEMENT
For grade 1	No anti-HTN therapy, no change in sorafenib dose
For grade 2	Initiate monotherapy with anti-HTN medication, no change in sorafenib dose
For grade 3	Add additional agent for anti-HTN therapy, hold sorafenib dose. Restart if blood pressure comes back in range for age, gender then dose reduce sorafenib to 100 mg/m ² /day
For grade 4	Permanently discontinue sorafenib

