The mean elimination half-life of sorafenib is approximately 25 to 48 hours. Multiple dosing of sorafenib for 7 days resulted in a 2.5 to 7-fold accumulation compared to single dose administration. Steady-state plasma sorafenib concentrations are achieved within 7 days, with a peak-to-trough ratio of mean concentrations of less than 2. A study of the pharmacokinetics of sorafenib indicated that the mean AUC of sorafenib in Asians (N=78) was 30% lower than the mean AUC in Caucasians (N=40). In adult patients, gender and age do not appear to have a clinically meaningful effect on the pharmacokinetics of sorafenib. In children with refractory solid tumors or leukemias, single agent sorafenib pharmacokinetics were similar to adults. Significant interpatient variability was observed both on Day 1 and at steady state. Drug exposure increased only marginally with dose escalation from 150 to 200 mg/m² for day 1 pharmacokinetics. The terminal half-life in children appeared to be prolonged (\geq 24 hours) but could not be estimated. Sorafenib accumulated after multiple doses and steady state appeared to be achieved after 5 to

7 days. Steady-state sorafenib concentrations (AUC_{0-12h/12}) were $4.1 \pm 2.1 \mu\text{g}/\text{mL}$ at the 150 mg/m² and $5.4 \pm 1.8 \mu\text{g}/\text{mL}$ at 200 mg/m² dose levels, respectively. The median apparent sorafenib clearance at the MTD was 56.0 mL/min/m². The apparent sorafenib clearance increased with patient age. The observed single agent sorafenib MTD in pediatric patients was 200 mg/m²/dose twice daily for solid tumors and 150 mg/m²/dose twice daily for leukemias. The pharmacokinetics of sorafenib in patients with varying degrees of renal and hepatic impairment have been studied. No dose adjustment is necessary in patients with renal impairment or with mild to moderate hepatic impairment.

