NERVOUS SYSTEM DISORDERS		
	Dizziness	
	Headache	
		Intracranial hemorrhage
		Reversible posterior leukoencephalopathy syndrome
PSYCHIATRIC DISORDERS		
	Insomnia	
RENAL AND URINARY DISORDERS		
	Acute kidney injury	
RESPIRATORY, THORACIC AND MEDIASTINAL DISORDERS		
	Cough	
	Dyspnea	
	Respiratory hemorrhage	
	Voice alteration	
SKIN AND SUBCUTANEOUS TISSUE DISORDERS		

Adverse Events with Possible Relationship to Sorafenib (BAY 43-9006; Nexavar) (CTCAE 4.0 Term) [n= 2571]		
Likely (>20%)	Less Likely (<=20%)	Rare but Serious (<3%)
Alopecia		
	Dry skin	
		Erythema multiforme
Palmar-plantar erythrodysesthesia syndrome		
	Pruritus	
Rash maculo-papular		
		Stevens-Johnson syndrome
		Toxic epidermal necrolysis
VASCULAR DISORDERS		
	Hypertension	
		Thromboembolic event

Formulation and Stability:

Sorafenib is supplied as a yellow-orange 50 mg and a red-colored 200 mg, round, immediate-release filmcoated tablet containing the excipients croscarmellose sodium, microcrystalline cellulose, hydroxypropylmethylcellulose, sodium lauryl sulfate, and magnesium stearate. The 200 mg film-coat consists of hydroxypropylmethyl cellulose, polyethylene glycol, titanium dioxide and red iron oxide. The 50 mg film-coat consists of hypromellose, PEG 3350, titanium dioxide, and yellow ferric oxide. The film coating has no effect on active BAY 43-9006 tosylate release rate.

Sorafenib 200 mg tablets are supplied in high-density polyethylene (HDPE) bottles of 140 tablets and the 50 mg tablets are supplied in HDPE bottles of 100 tablets. The bottles should be stored at controlled room temperature (15-25°C; 59-77°F) and storage temperature should not exceed 25°C (77°F). Stability testing is ongoing.

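### Appendix I's lowest sorafenib row (BSA 0.35 m² or less) has no lower limit, so below about 0.29 m² it exceeds the ordered 200 mg/m²/day by more than any closed row of the table does

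*Combined protocol and SAP*

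**What the plan says.** Section 5.2 sets the sorafenib order for FLT3-ITD patients: "Dose: 200 mg/m²/dose daily, rounded to accommodate tablet size", with a 400 mg maximum. It then makes the table operative: "Dose will be administered per dosing nomogram in Appendix I". Section 5.4 does the same ("Dose to be administered per dosing nomogram in Appendix I"), and Sections 5.6 and 5.8 repeat the dose and the reference.

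In Appendix I, the first row covers every BSA of 0.35 m² or less. Its Dose Level 1 (200 mg/m²/day) cell reads "50 mg x 5 days/week, 100 mg x 2 days/week (450 mg" per week). Its Dose Level 0 (100 mg/m²/day) cell reads "50 mg x 4 days/week, 0 x 3 day/week (200 mg" per week). Level 0 matters because Section 6 uses it for toxicity. After a cardiac hold, for example, Section 6.3.3 says "Sorafenib should be restarted at a reduced dose", namely 100 mg/m².

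The nomogram, the sorafenib paragraphs and Section 6 state no smallest BSA. Section 3.1.1 sets only an upper age limit. Section 5.2 lists an intrathecal dose for the first year of life, so infants are in scope. The IV chemotherapy drugs and gemtuzumab change to per-kilogram dosing below 0.6 m²; sorafenib has no such rule. On tablet strength, Section 9.6 states: "Sorafenib is supplied as a yellow-orange 50 mg and a red-colored 200 mg".

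**The concern.** A fixed weekly amount over a band with no lower end means that the dose per m² rises as the child gets smaller. The other open row, at 1.86 m² and above, is explained by the 400 mg maximum. No rule in the protocol plays that part at the bottom.

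A prescriber who follows the table for a very small infant with FLT3-ITD would therefore give more than the treatment sections order, by more than tablet rounding produces elsewhere in the same table. The reduced level used after toxicity is open in the same way. What is at stake is the dose given to an individual infant. The EFS estimate and the other analyses are not affected.

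**Working it through.** **Inputs.** From Appendix I: the BSA bands and weekly totals. From Sections 5.2 to 5.8: the 200 mg/m²/day target. From Section 9.6: the 50 mg tablet and the single-agent leukemia MTD. The BSA values inside the lowest row are assumptions.

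**Formula.** Average mg/m²/day = weekly mg ÷ 7 ÷ BSA. Weekly averages are the right measure because the table rounds by mixing tablet counts across the week.

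**Reproducing the plan's figure.** 5 × 50 + 2 × 100 = 450 mg/week, as printed. All 15 Dose Level 1 totals reproduce exactly.

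**The table's own rounding at Dose Level 1 (rows with both limits).**

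| BSA band (m²) | mg/week | mg/m²/day at low edge | at high edge |
|---|---|---|---|
| 0.36-0.40 | 500 | 198.4 | 178.6 |
| 0.41-0.45 | 600 | 209.1 | 190.5 |
| 0.46-0.55 | 700 | 217.4 | 181.8 |
| 0.56-0.60 | 800 | 204.1 | 190.5 |
| 0.61-0.70 | 900 | 210.8 | 183.7 |
| 0.71-0.80 | 1050 | 211.3 | 187.5 |
| 0.81-0.90 | 1200 | 211.6 | 190.5 |
| 0.91-1.05 | 1400 | 219.8 | 190.5 |
| 1.06-1.20 | 1600 | 215.6 | 190.5 |
| 1.21-1.35 | 1750 | 206.6 | 185.2 |
| 1.36-1.60 | 2100 | 220.6 | 187.5 |
| 1.61-1.70 | 2450 | 217.4 | 205.9 |
| 1.71-1.85 | 2650 | 221.4 | 204.6 |

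The closed rows run from 178.6 to 221.4, about 11% either side of 200. Twelve of the 13 exceed 200 at their low edge.

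**The lowest row at Dose Level 1.** 450 ÷ 7 = 64.29 mg/day.

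| Assumed BSA (m²) | mg/m²/day | against 200 |
|---|---|---|
| 0.35 | 183.7 | -8% |
| 0.32 | 200.9 | +0.4% |
| 0.30 | 214.3 | +7% |
| 0.29 | 221.7 | +11% |
| 0.28 | 229.6 | +15% |
| 0.25 | 257.1 | +29% |

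Crossing points:
- It passes 200 at 64.29 ÷ 200 = 0.321 m².
- It passes the closed-row maximum at 64.29 ÷ 221.4 = 0.290 m².
- It passes 300 mg/m²/day at 64.29 ÷ 300 = 0.214 m². The 300 is Section 9.6's "150 mg/m²/dose twice daily for leukemias", doubled to a daily total.

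**Does tablet size force this?** No. At 0.25 m², one 50 mg tablet a day is 50 ÷ 0.25 = 200 mg/m². Over 0.23-0.28 m² that schedule gives 50 ÷ 0.23 = 217.4 down to 50 ÷ 0.28 = 178.6, which is inside or level with the closed-row range. At 0.22 m² it gives 227.3, outside the range.

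**Dose Level 0.** The closed rows run from 89.3 to 109.9. The lowest row gives 200 ÷ 7 = 28.57 mg/day. That passes 100 at 0.286 m² and 109.9 at 0.260 m², and gives 114.3 at 0.25 m².

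**The case against.** **It may affect nobody.** The documents do not say how small an enrolled infant would be. Section 2.4 puts activating FLT3 mutations at about 15% of pediatric AML; with about 30 patients, 0.15 × 30 = 4.5 across all ages under 21, and Section 2.4 restricts sorafenib further to an allelic ratio above 0.1. This stands. It limits the weight of the point but does not make the row right for a patient who falls in it.

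**The order allows rounding, and the table is how the dose is given.** This stands down to about 0.29 m². A reader might infer that the row overdoses every child below 0.32 m², because it passes 200 there. The documents do not support that: between 0.29 and 0.32 m² the excess is no larger than other rows accept. The 0.29 m² cut-off is itself a benchmark taken from the table's closed rows, not a tolerance that the protocol states.

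**The arithmetic is sound.** This also stands. A reader might infer a calculation error in Appendix I, but every Dose Level 1 total checks.

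**The consequence is limited.** The average dose stays under 300 mg/m²/day down to 0.214 m². Section 6 has hold, reduce and stop rules for cardiac toxicity, hypertension and skin toxicity. A reader might picture excess sorafenib on the same days as IV chemotherapy. The schedules show otherwise: within each course, sorafenib starts after the last IV chemotherapy day (day 11 after days 1-10, day 7 after days 1-6, day 6 after days 1-5, day 11 after days 1-9). The MTD is for sorafenib alone, so it is context and not evidence that the higher dose is safe after intensive chemotherapy. None of these points closes the row.

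**Conclusion.** The point holds as a gap in table design. For BSA below about 0.29 m², following Appendix I delivers more than the ordered 200 mg/m²/day, beyond the 179-221 spread of the closed rows: 230 at 0.28 m² and 257 at 0.25 m². Dose Level 0 has the same gap below 0.26 m².

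This rests on two things: reading the lowest row literally, since nothing in the protocol bounds it, and assumed BSA values. The documents do not show that any sorafenib-eligible patient will be that small. A reader might go further and infer that the trial's safety or efficacy results are compromised; nothing supports that, because few or no patients are expected and no endpoint, sample size or analysis depends on this row. It is a small correction worth making, no more.

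**What to change.** In Appendix I, relabel the lowest row 0.29-0.35 m² and add one footnote along these lines:

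*BSA below 0.29 m²: do not use this row; confirm the dose with the Study Chair and pharmacy before starting or reducing sorafenib. For Dose Level 1, 50 mg once daily gives 217-179 mg/m²/day at 0.23-0.28 m².*

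One cut-point for both dose levels keeps the shared BSA column simple. Separate limits for Level 1 (0.29 and 0.23 m²) and Level 0 (0.26 m²) would split the one row into four bands. The price is slight caution at Level 0: from 0.26 to 0.28 m² the present 200 mg/week (109.9 to 102.0 mg/m²/day) is within that level's range but would still need confirmation.

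The cost is one label, one footnote and a pharmacy check of the wording. In use, it adds a brief dose-confirmation step for a very small infant.
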